#### 9.5.3. **Attempt**

An attempt subject is one who signs informed consent, meets eligibility criteria, and has any study device inserted into the body but does not receive ablation (RF energy) with the StablePoint Catheter System. Attempt subjects will be used for analysis of the primary safety endpoints and additional analyses of safety data, but attempt subjects will not be used for analysis of the primary effectiveness endpoints or additional analyses of effectiveness data (additional analysis include subgroup, multivariable, and center pooling analyses). Attempt subjects do not count toward the enrollment ceiling.

The original signed Informed Consent and any relevant documentation must be maintained in the site's subject file. A subject ID will be assigned in the EDC system. Attempt subjects are not allowed to be re-enrolled in the study.

Attempt subjects will be followed up to 30 days for safety. Subjects will not need to complete post-procedure arrythmia monitoring as these subjects will not count toward the analysis of the effectiveness endpoints. All applicable case report forms, per the protocol, will be completed.

For attempt subjects, at the miniumum the following forms must be completed:

- Enrollment and baseline forms such as, but not limited to: informed consent, enrollment information and other related forms;
- End of Study form;
- Protocol Deviation form
- Adverse Event forms for any reportable event, as defined in Section 18.1 for any adverse event that occurs after signing the Informed Consent, up to the point of subject withdrawal

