Enapoints	
 
Secondary Safety Endpoint – SAE and AE Rates
 
Secondary Effectiveness Endpoint 1 – New or Increased Dose of AAD
 
				
	
 
Secondary Effectiveness Endpoint 2 – Single Procedure Success defined as freedom from primary effectiveness failure without a repeat procedure
 
Secondary Effectiveness Endpoint 3 – Symptomatic Recurrence: freedom from documented symptomatic AF/AT/AFL recurrence
 
				
Additional	Other additional endpoints and analysis include, but are not limited to:				
Endpoints	
 
Changes in the quality of life measures (AFEQT and EQ-5D-5L) between baseline and 12 months follow up
 
				
	
 
Total RF time for the index procedure (defined as the summation of all RF application durations)
 
				
	Total number of RF applications				
	
 
Total fluoroscopy time for the index procedure
 
				

Cli n ical E valu	nation of the StablePoint Catheter and Force-Sensing System for Paroxysmal Atrial Fibrillation
	(NEWTON AF)
	
 
Total index procedure time
 
Freedom from recurrence of individual types of atrial arrhythmias between 91 and 365 days from index procedure: 1) AF 2) AT 3) AFL
 
Freedom from cardiovascular hospitalization at 12 months
 
Quantification of parameters used during RF Application including RF power, RF duration, contact force and Local Impedance via DIRECTSENSE™ technology
 
Descriptive summaries of primary safety and effectiveness endpoints at 12 months using the data available at the time of the 6-month analysis
 
The predicted probability of success for the primary effectiveness endpoint at 12 months based off the data available at the time of the 6-month analysis.
 

Method of Assigning Subjects to Treatment	Any subject that signs the consent form, meets eligibility criteria, has the study device inserted into the body and receives ablation therapy will be assigned to the TREATMENT group.
Follow-up Schedule	Subjects will complete a pre-discharge visit, 1-month, 3-month, 6-month, and 12-month visit.
Study Duration	Enrollment is expected to be completed in approximately 12 months; therefore, the total study duration is estimated to be approximately 24 months.
Participant Duration	The study duration for each subject is expected to be approximately 12 months.

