# 6.3. Primary Effectiveness Endpoint at 6 Months

The primary effectiveness endpoint at 6 months is defined as the effectiveness event-free rate at 6 months (183 days) post-procedure. If the analysis of the primary effectiveness endpoint at 6 months is not passed, then effectiveness may be re-evaluated via the primary effectiveness endpoint at 12 months, as described in Section 6.6.

Primary effectiveness events at 6 months are defined as:

- Acute procedural failure
  - Failure to achieve acute procedural success in the index procedure or in a repeat procedure during the blanking period.
  - Acute procedural success is defined as the achievement of electrical isolation of all PVs using the StablePoint catheter only. Electrical isolation of a PV is demonstrated by entrance block after 20 minutes waiting period. If exit block testing is performed, the PV will only be considered as isolated if both entrance and exit block testing are successful.

- Use of amiodarone post index procedure
- Use of non-study ablation catheter in the index procedure or in a repeat procedure during the blanking period
- More than one repeat procedure during the blanking period (90 days post index procedure)
- Surgical ablation of Atrial Fibrillation (AF)/Atrial Tachycardia (AT)/Atrial Flutter (AFL) post index procedure
- Documented atrial fibrillation, or new onset of atrial flutter or atrial tachycardia between 91 days and 183 days post index procedure captured by one of the following methods:
  - > 30 seconds in duration recording from the study specific event monitor or Holter Monitor
  - ≥ 10 second 12-lead Electrocardiography (ECG)
- Any of the following interventions for atrial fibrillation, or new onset of atrial flutter or atrial tachycardia between 91 days and 183 days post index procedure:
  - Repeat procedure
  - Electrical and/or pharmacological cardioversion
  - Prescribed any AAD\*
- \*AADs for endpoint will consist of all Class I/III, including Amiodarone, and any Class II/IV medications taken for control of atrial fibrillation (AF)/Atrial tachycardia (AT)/Atrial flutter (AFL) recurrence.

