#### 9.5.4. Treatment

Any subject that signs the consent form, meets eligibility criteria and has the specified study device inserted into the body and receives RF ablation with the StablePoint Catheter System will be classified as "TREATMENT". These subjects are followed in accordance with the follow-up schedule and are included in all study analyses. A subject ID will be assigned in the EDC system.

All applicable case report forms, per the protocol, must be completed for TREATMENT subjects. TREATMENT subjects do count towards the enrollment ceiling and will be used for analyses of the endpoints. The original signed Informed Consent and any relevant documentation must be maintained in the center's patient file.

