#### 11.3. General Statistical Methods

### 11.3.1. Analysis Sets

While each endpoint was individually powered, each safety endpoint analysis will use all available data from all ATTEMPT and TREATMENT subjects, and each effectiveness endpoint analysis will use all available data from all TREATMENT subjects.

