Any subject that signs the consent form, meets eligibility cri Treatment Subject the specified study devices inserted into the body and under specific treatment for the intended disease.			
Vagal Nerve Injury/Gastroparesis	Vagal nerve injury is defined as injury to the vagal nerve that results in esophageal dysmotility or gastroparesis. Vagal nerve injury is considered to be a major complication if it prolongs hospitalization, requires hospitalization, or results in ongoing symptoms for more than 30 days following an ablation procedure		
Development of a hematoma, an AV fistula, or a pseudoaneur major vascular complication is defined as one that requires int such as surgical repair or transfusion, prolongs the hospital star requires hospital admission.			

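### Subjects in whom StablePoint is inserted but delivers no RF, and who are then ablated with a non-study catheter, drop out of every effectiveness endpoint, so acute success can only be biased upward

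*Combined protocol and SAP*

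**What the plan says.** **Classification.** Section 9.5.3 defines an ATTEMPT subject as one who "has any study device inserted into the body but does not receive ablation (RF energy) with the StablePoint Catheter System". It does not ask whether another catheter was used afterwards. Section 9.5.4 is the mirror image: a subject who "receives RF ablation with the StablePoint Catheter System will be classified as" TREATMENT.

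**Consequence.** Section 9.5.3 states that "attempt subjects will not be used for analysis of the primary effectiveness endpoints". ATTEMPT subjects are followed for 30 days without arrhythmia monitoring, because "these subjects will not count toward the analysis of the effectiveness endpoints". They stay in the safety analyses and do not count toward the enrollment ceiling. Section 11.3.1 confirms that "each effectiveness endpoint analysis will use all available data from all TREATMENT subjects". The Table 26-2 entry for primary effectiveness failure is also confined to TREATMENT subjects.

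**Endpoint.** Section 6.2 grants acute success only if every pulmonary vein is isolated with the study catheter alone. Sections 6.3 and 6.5 list as a failure "Use of non-study ablation catheter in the index procedure or in a repeat procedure during the blanking period".

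**Rows that name no catheter.** The synopsis row on assigning subjects says that an eligible, consented subject who "has the study device inserted into the body and receives ablation therapy will be assigned to the TREATMENT group". The TREATMENT row of Table 26-2 (section 26.2) speaks of "the specified study devices inserted into the body and under specific treatment for the intended disease".

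**The concern.** Take two subjects at the index procedure. In the first, StablePoint delivers one RF application and the operator then finishes with another catheter. In the second, StablePoint is inserted, delivers nothing, and the operator finishes with the same other catheter. The first is TREATMENT and fails acute success and both later endpoints. The second is ATTEMPT and is counted in none of them.

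The endpoint asks whether the study catheter alone can isolate all the veins, and the second subject answers that at least as clearly as the first. Section 10.7 adds to the contrast: not using StablePoint in a repeat procedure during blanking is an endpoint failure.

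Entry to the denominator thus depends on the device having first delivered energy, and a single-arm trial has no comparator in which the same selection would occur. Acute success is required in every success case in 6.6.1 and 6.6.2, so an inflated rate bears directly on the study conclusion.

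**Working it through.** **Inputs.** From 11.1.2.2 and 11.1.2.3: expected rate 98%, goal 92%, one-sided 2.5%, power 90%, Clopper-Pearson lower limit, stated N = 160. From 7.1: 299 TREATMENT subjects. Assumed: k subjects with StablePoint inserted, no StablePoint RF and another catheter used. The documents do not give k. Since ATTEMPT subjects are outside the ceiling, these k come on top of the 299.

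**Formula.** For x successes in n, the lower limit is L = Beta⁻¹(0.025; x, n − x + 1). The endpoint passes if L > 0.92.

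**Step 1: the plan's own figure.** At n = 160 the rule needs at least 154 successes, with exact alpha 0.0246 and power 95.7%. Power first reaches 90% at n = 143 but falls below it again, last at n = 159 (89.9%). So 160 is the smallest n from which power stays at or above 90%, and the stated size reproduces.

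**Step 2: the rule at 299.** A pass needs at least 285 successes (at most 14 failures): 285/299 gives L = 92.27%. Exact alpha is 1.7%, and power at 98% is 99.9%.

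**Step 3: chance of passing if the rate with all such subjects counted is exactly 92%.** The k subjects are certain failures, so the rate among the 299 is p = 0.92 × (299 + k)/299. The chance of passing is P(Bin(299, p) ≥ 285).

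| k | p | Chance of passing |
|---|---|---|
| 0 | 92.00% | 1.7% |
| 1 | 92.31% | 2.6% |
| 3 | 92.92% | 6.0% |
| 6 | 93.85% | 17.5% |

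One such subject is enough to pass the nominal 2.5%.

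**Step 4: result at the planned rate.** 0.98 × 299 ≈ 293 successes, so about 6 failures. Adding k failures:

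| k | Observed | Rate | L | Result |
|---|---|---|---|---|
| 0 | 293/299 | 98.0% | 95.7% | pass |
| 3 | 293/302 | 97.0% | 94.4% | pass |
| 6 | 293/305 | 96.1% | 93.2% | pass |
| 9 | 293/308 | 95.1% | 92.09% | pass |
| 10 | 293/309 | 94.8% | 91.73% | fail |

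**Step 5: power if the 299 succeed at 98% and the k are counted as failures.** 99.9% at k=0, 98.2% at k=3, 92.0% at k=6, 61.0% at k=9.

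**Step 6: later endpoints, k = 6, treated as simple proportions.** 72% × 299/305 = 70.6%, and 60% × 299/305 = 58.8%. Both shifts are small against goals of 60% and 50%.

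**The case against.** *The analysis set is openly pre-specified.* That is true: 9.5.3 and 11.3.1 state who is in each set, and restricting effectiveness to subjects who received study RF is a choice of estimand. But it sits badly with an endpoint that defines success as isolation by this catheter alone and already counts a switch as failure.

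*A reader might infer two competing rules,* TREATMENT in the synopsis and ATTEMPT in 9.5.3, giving two primary results from the same data. The documents do not support this. The synopsis row is silent on the catheter, not contrary. Elsewhere the synopsis describes TREATMENT subjects as treated with StablePoint, 7.2.1 requires StablePoint for all ablations, and 9.5.4 and the glossary ATTEMPT row agree with 9.5.3. The glossary TREATMENT row is broken in the available text and is weak evidence. What remains is a wording gap.

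*A reader might take all ATTEMPT subjects to be device failures.* They are not. The category covers any study device inserted without StablePoint RF, for any reason. An unreachable vein would normally still leave RF at other veins, which makes the subject TREATMENT and a failure. Section 10.6.2.2 also allows several catheter curves without penalty.

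*A single subject can reverse the result.* Only at the boundary: 285/299 passes and 285/300 gives L = 91.89%. At a true 98%, the chance that counting k such subjects turns a pass into a fail is 0.2% for k=1, 1.7% for k=3 and 7.9% for k=6.

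*Comparability with the goals.* In the sponsor's tables several arms have fewer subjects for 6-month effectiveness (11.1.3.2) than for safety (11.1.1.2): 122 against 161, 146 against 152, 134 against 143, 167 against 172. The reasons are not given, so a wider set here might be less comparable with the 6-month goal. This is a reason to keep the RF-delivered set as supportive. It does not extend to the acute goal, which comes from a different source.

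*The subjects are not hidden.* They remain in the safety analyses, on the screening and enrollment log and on deviation forms. That helps reporting but does not change the primary effectiveness rates.

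**Conclusion.** The point holds as a defect in the effectiveness analysis set. Under the intended rule (9.5.3, 9.5.4, 11.3.1), a switch to a non-study catheter before any StablePoint RF is not counted, while the same switch after one application is a failure. Each such subject counted would add to the denominator and not to the successes, so leaving them out can only raise the acute success rate.

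The size depends on k, which the documents do not give. If k is 0, nothing changes. If the true rate is at the goal, small numbers already matter: k=1 takes the chance of a false pass from 1.7% to 2.6%, and k=6 takes it to 17.5%. If the catheter performs as planned, the conclusion is robust up to 9 such subjects and reverses at 10. The effect on the 6- and 12-month rates is small. These figures assume 299 TREATMENT subjects, k further subjects each scored as a failure, and independent outcomes.

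**What to change.** 1. In 9.5.3 and 11.3.1, for the primary effectiveness endpoints, include every eligible subject in whom StablePoint was inserted and a non-study catheter was then used for ablation in the index procedure. Score each as an acute procedural failure on day 0. The criterion is objective and is already a listed failure component, so it needs no adjudication of cause.
2. Report the present RF-delivered TREATMENT set as supportive.
3. Report the number of all other ATTEMPT subjects with their reasons. Add a sensitivity analysis that counts those stopped for a reported device deficiency as failures. This belongs in a sensitivity analysis because attributing a stop to the device is a judgement, and no effectiveness adjudicator is named.
4. Align the synopsis TREATMENT row and the Table 26-2 TREATMENT row with 9.5.4 by naming the catheter, and cross-refer to the inclusion rule in item 1.
5. Confirm that the index-procedure form, with non-study devices used and the reason for no RF, is completed for ATTEMPT subjects. The minimum list in 9.5.3 does not name it.

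The cost is protocol and SAP wording plus that form check. The event is dated day 0, so no added follow-up or rhythm monitoring is needed. The downside is slightly less favourable acute and effectiveness rates. The change should be made before the number and outcomes of these subjects are known.

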#### 9.5.4. Treatment

Any subject that signs the consent form, meets eligibility criteria and has the specified study device inserted into the body and receives RF ablation with the StablePoint Catheter System will be classified as "TREATMENT". These subjects are followed in accordance with the follow-up schedule and are included in all study analyses. A subject ID will be assigned in the EDC system.

All applicable case report forms, per the protocol, must be completed for TREATMENT subjects. TREATMENT subjects do count towards the enrollment ceiling and will be used for analyses of the endpoints. The original signed Informed Consent and any relevant documentation must be maintained in the center's patient file.

## 9.6. End-of-Study Definition

A clinical trial is considered completed when subjects are no longer being examined or the last subject's last study visit has occurred.

A subject is considered to have completed the study if he or she has completed all phases of the study including the last visit or assessment as shown in the Data Collection Schedule (Table 10-1).

The end of the study is defined as completion of the last visit shown in the Data Collection Schedule including the 12-month follow-up visit and 24-hour Holter Monitor.

# 10. Study Methods

#### 10.1. Data Collection

Each TREATMENT subject will be followed per the Data Collection Schedule defined in Table 10-1.

Table 10-1: Data Collection Follow-up Schedule

	I			Blanking Period			Effectiv	eness Evaluation	Other		
Procedure/ Assessment	Enrollment (up to 30 days prior to Index Procedure)	Baseline (up to 30 days prior to Index Procedure)	Index Procedure (Day 0)	Pre- Discharge Follow-Up (0 -7 D Post- Index Procedure)	1M Follow-Up (30 ± 10 D Post Index Procedure)	Repeat- Procedure (≤ 90 D Post- Index Procedure)	3M Follow-Up (91±14 D Post Index Procedure)	6M Follow-Up (180 + 30 D Post Index Procedure)	12M Follow-Up (365 ± 30 D Post Index Procedure)	Unsched. Follow- Up	Repeat- Procedure (>91 D Post- Index Procedure)
Informed consent process, including informed consent signature date	x	1		-	-		-	1	1	-	-
Eligibility Criteria	X	X	X	-	-		-	-	-	-	
Pregnancy Test, if necessary		X	-				-	ı	ı	-	
Demographics		X						-	-		
Medical history		X	-					1	1	-	
Physical Assessment		X		X	X		X	X	X	X	
Blood Tests		$X^{l}$					-	1	1	-	
Cardiovascular/Pulmonary Exam		X		X	X			-	-		
Quality of Life Questionnaires (EQ-5D-5L and AFEQT)		x	-	-	-	-	X 	X 	X 	-	-
NIH Stroke Scale (NIHSS)		X		X 	-	X 6	-	-	-		X 6
Cardiac CT or MRI to assess PV diameter/stenosis		х	-	X 	X 		X 	X 	X 	X 	
Neurology Consultation		-		X 		X 		-	-		X 
Echocardiography to assess cardiac size and function		x²						-	-		
Screening for LA thrombus (TEE/ICE)		x³	x³			x³		1	1	-	x³
Procedural Data		-	X			X		-	-	-	X
RHYTHMIA HDx Export (Electronic Case Data)		1	Х	-		x	-	1	1		х
12-Lead ECG		X	X	X	X	X	X	X	X	X	X
Phrenic Nerve Palsy Assessment				X8	X8	X8	X8	X8	X8	X8	X8

				Blanking Period			Effectiv	eness Evaluatio	Other		
Procedure/ Assessment	Enrollment (up to 30 days prior to Index Procedure)	Baseline (up to 30 days prior to Index Procedure)	Index Procedure (Day 0)	Pre- Discharge Follow-Up (0 -7 D Post- Index Procedure)	1M Follow-Up (30 ± 10 D Post Index Procedure)	Repeat- Procedure (≤ 90 D Post- Index Procedure)	3M Follow-Up (91±14 D Post Index Procedure)	6M Follow-Up (180 ± 30 D Post Index Procedure)	12M Follow-Up (365 ± 30 D Post Index Procedure)	Unsched. Follow- Up	Repeat- Procedure (>91 D Post- Index Procedure)
Holter Monitor (24H)		1	-		-			X	X		
Arrhythmia/Event Monitor		-	-	X	X		X	X	X	X	
Documentation of intervention AF/AT/AFL (if any)		-	-	-	Х	х	Х	Х	Х	х	X
Device Deficiency Assessment		-	X		-	X	-	-	-		x
Medications (AAD/Anticoagulants)	X	X	X	X	X	X	X	X	X	X	X
Adverse Events Assessment	X	X	X	X	X	X	X	X	X	X	X
Protocol Deviations	X	X	X	X	X	X	X	X	X	X	X

X = required; --= not required

Abbreviations: D = day(s), H = hour(s), NIH = National Institutes of Health, ECG = electrocardiogram, M = Month, TTE = trans-thoracic echocardiogram, TEE = trans-esophageal echocardiogram, CT = Computed Tomography, MRI = Magnetic Resonance Imaging

<sup>1Blood tests up to 90 days prior to enrollment

<sup>2TTE/TEE only required if data not available within 180 days prior to enrollment (See Section 10.6.1 for additional details on test requirements)

<sup>3 TEE within 48 hours prior to the index procedure or ICE during the procedure. For subjects that are unable to undergo TEE, ICE may be considered as an alternative

<sup>4 Neurology consult is only required if NIHSS scale worsens from the previous assessment. If it is suspected the patient experienced a new cerebral ischemic event, a cerebral vascular imaging/DW-MRI scan is required and must be performed within local guidelines associated with brain MRI scan.

<sup>5Cardiac CT/MRI scan may be considered post-procedure if PV stenosis is suspected.

<sup>6NIHSS at Pre-Discharge must be performed between Day 1 and Day 7 after the procedure. All NIHSS assessments must be completed by a person certified in the administration of the NIHSS.

<sup>7Quality of Life Instruments (AFEQT and EQ-5D-5L) is highly recommended prior to the remaining clinical assessments (e.g., 12-lead ECG and physical assessment).

Phrenic Nerve Palsy Assessment at discharge and at follow-up visits is only applicable for subjects who had phrenic nerve palsy detected during the index or repeat procedure. Subjects should be assessed per standard of care; suggested means of assessment include a sniff test or an inhalation-exhalation chest radiography of the diaphragm.

## 10.2. Study Candidate Recruitment, Screening and Retention

Investigators are responsible for screening all subjects and selecting those whom are appropriate for study inclusion. The subjects selected for participation should be from the investigator's general patient population. The investigator is expected to follow standard of care testing to diagnose and screen subjects for inclusion in the study. Subjects may be given a subject stipend for their time completing study assessments.

### 10.2.1. Screening and Enrollment Log

A Screening and Enrollment Log will be maintained to document select information about candidates who fail to meet the general and specific selection criteria, including those enrolled in the study and classified either as Consent Ineligible, Intent, Attempt or TREATMENT subjects.

#### 10.3.Informed Consent and Enrollment

Subjects who have signed and dated the Informed Consent Form are considered enrolled in the study. In order to determine eligibility of a subject, the investigator or designee needs to implement the consent process as well as verify and document the subject meets final eligibility criteria prior to receiving RF ablation therapy in the NEwTON AF study. Informed consent is required for all subjects prior to their participation in the study. No study-specific procedures can be conducted prior to the subject providing his/her consent.

The subject will be given ample time to consider participation and ask questions if necessary. An approved informed consent form (ICF) shall be signed and personally dated by the subject. The original, signed consent must be kept with the subject's file and a copy must be provided to the subject.

The index procedure must be performed within 30 days post ICF signature. In case the index procedure has not been performed within this time period, the subject will be classified as Intent (see Section 9.5.2). The same subject cannot be considered for re-enrollment as reenrollment is not allowed for any subjects in this study. The site will ensure that originally signed ICFs are filed in subjects' binders and the ICF process is properly documented in the medical file. Originally signed ICFs and the ICF process will be made available for review at Monitoring Visits (MVs).

For additional information regarding the informed consent process, refer to Section 9.

